## Revision History

Version	Date	Reason for update
V3.0	03/12//2018	
Terminology has been made consistent throughout the document: the Study Coordination Centre referring to Imperial College London and Clinical Trials Unit referring to Centre for Randomised Trials Aberdeen.
 
'Moderate risk' has replaced all instances of 'medium or intermediate risk' throughout the document
 
The flow chart has been updated to add secondary outcome text 'overall mortality' which was not included in the original flow diagram
 
Section 7.4 has been updated to reflect changes to the statistical analysis based on the low number of events reported throughout the study
 
Addition of wording to explain that a time only no cost extension of 12 months was approved by the Funder
 
Tightening of the terminology- the word composite outcome has been removed to accurately reflect the outcome measure being used.
 
A sentence has been added to say that data collected by the trial team for the duplex scan outside of the 14-21 day window will be recorded by the trial coordinating centre and analysed
 
Addition of Appendix 3 summarising the rationale for the statistical changes made to the study

V2.1	17/03/2016	To change wording from 'post-randomisation' to 'post-surgery'
V2.0	04/02/2016	Changes made from v1.0 to submit to REC for approval.
V1.0		N/A- draft version of the protocol not submitted to REC

## Funder

This project is funded by the National Institute for Health Research Health Technology Assessment (HTA) Programme (project number 14/140/61)

This protocol describes the **Graduated compression as an Adjunct to Pharmacoprophylaxis in Surgery (GAPS) trial**. Every care was taken in its drafting, but corrections or amendments may be necessary. These will be circulated to investigators in the study. Problems relating to this study should be referred, in the first instance, to the Chief Investigator.

This study will adhere to the principles outlined in the NHS Research Governance Framework for Health and Social Care (2nd edition, or subsequent). It will be conducted in compliance with the protocol, the Data Protection Act and other regulatory requirements as appropriate.

## GLOSSARY OF ABBREVIATIONS

AE	Adverse Event
CHaRT	Centre for Healthcare Randomised Trials
CI	Chief Investigator
CNORIS	Clinical Negligence and Other Risks Scheme
CRF	Case Report Form
CTU	Clinical Trials Unit
DVT	Deep Vein Thrombosis
EQ-5D	EuroQuol 5 Domain
GAPS	Graduated compression as an Adjunct to Pharmacoprophylaxis in Surgery
GCP	Good Clinical Practice
GCS	Graduated Compression Stockings
LMWH	Low Molecular Weight Heparin
HTA	Health Technology Assessment
iDMC	Independent Data Monitoring Committee
IPC	Intermittent Pneumatic Compression
ISF	Investigator Site File
IT	Information Technology
ITT	Intention to Treat
IVC	Inferior Vena Cave
JCRO	Joint Compliance Research Office
LPLV	Last Patient Last Visit
NICE	The National Institute for Health and Care Excellence
NHS	National Health Service
NIHR	National Institute for Health Research

PI	Principal Investigator
PE	Pulmonary Embolism
PROM	Patient Reported Outcome Measure
RCT	Randomised Controlled Trial
R&D	Research & Development
REC	Research Ethics Committee
QA	Quality Assurance
SAE	Serious Adverse Event
SAP	Statistical Analysis Plan
SOP	Standard Operating Procedure
SSA	Site Specific Assessment
SUSAR	Suspected Unexpected Serious Adverse Reaction
SCC	Study Coordinating Centre
TMF/SMF	Trial/Study Master File
TSC	Trial Steering Committee
VTE	Venous Thromboembolism

## KEYWORDS

Surgery, Venous Thromboembolism, Deep Vein Thrombosis, Thromboprophylaxis, Graduated Compression Stockings, Pulmonary Embolism

## TRIAL SUMMARY

**TITLE** **Graduated compression as an Adjunct to Pharmacoprophylaxis in Surgery (GAPS) Trial**

**DESIGN** Multicentre-centre, UK-wide, open, randomised controlled trial. Non-inferiority, group sequential trial design.

**AIMS** The aim is to determine whether low dose low molecular weight heparin (LMWH) alone is non-inferior to a combination of graduated compression stockings (GCS) and low dose LMWH for the prevention of venous thromboembolism (VTE) adult elective surgical inpatients identified as being at moderate and high risk for VTE. The primary clinical objective is to compare the VTE rate in elective surgical inpatients receiving GCS and LMWH, compared with LMWH alone.

Other objectives include:

- To profile the adverse effects of GCS and LMWH anticoagulation in this context.
- To support future guidance and policy in VTE prevention.

## OUTCOME MEASURES

### Primary

VTE within 90 days {duplex ultrasound-proven new lower-limb DVT up to 90 days post-surgery (symptomatic or asymptomatic) and symptomatic PE (imaging confirmed) up to 90 days post-surgery}

### Secondary

- Quality of life – EQ5D
- Compliance with stockings and LMWH
- Overall mortality

### Safety

- GCS-related complications
- Bleeding complications
- LMWH allergy

**POPULATION** Elective surgical inpatients assessed as being at moderate or high risk of VTE according to the widely-used UK Department of Health VTE Risk Assessment for Venous Thromboembolism (based upon the NICE recommendations).

[figure not shown]
## ELIGIBILITY

### Exclusions

- Contraindications to LMWH/GCS
- Documented or known thrombophilia/thrombogenic disorder
- Requiring therapeutic anticoagulation
- Previous VTE
- Having intermittent pneumatic compression beyond theatre and recovery
- Patients requiring IVC filter
- Pregnancy
- Need extended VTE prophylaxis
- Cast/brace use

**DURATION** 48 months

## REFERENCE DIAGRAM (BASED ON ORIGINAL SAMPLE SIZE CALCULATION)

## 1. INTRODUCTION

### 1.1 BACKGROUND

At present, in the UK, NICE recommends that all surgical patients who are deemed at moderate or high risk for venous thromboembolism (VTE), in whom there are no contraindications, should receive both pharmacological thromboprophylaxis and mechanical thromboprophylaxis in the form of graduated compression stockings (GCS) (1). Are the risks and costs associated with GCS medically or health-economically justified for DVT prevention in moderate and high risk elective surgical inpatients receiving LMWH prophylaxis? VTE encompasses a range of clinical presentations, including pulmonary embolism, and is an important preventable cause of death in hospitalized patients (2). Furthermore, symptomatic venous thrombosis carries a considerable burden of morbidity, sometimes long-term due to chronic venous insufficiency. This in turn can cause venous ulceration and development of a post-thrombotic limb (characterised by chronic pain, swelling and skin changes), which impacts on quality of life and consumes 2% of the NHS budget (1). Treatment of non-fatal symptomatic VTE and related long-term morbidities is associated with a considerable cost to the health service (1). Reducing VTE is a clinical priority within the NHS (1), particularly amongst individuals undergoing surgery where the risks are significant. The risks need to be balanced against the risks of preventative measures, both mechanical and pharmacological. The evidence base supporting NICE's recommendations for the use of GCS for VTE prevention in the UK has recently been challenged (3,4). The main reasons include:

- The Cochrane Review (5) which showed a benefit for GCS included small trials (18-152 patients).
- Stocking manufacturer support of the included trials.
- Exclusion of two large trials from the Cochrane Review (in stroke (6) and orthopaedic patients (7)), one for being too specific a population, the other for being too pragmatic; neither of these studies supported the use of GCS (3).

Additionally, systematic review and meta-analysis data has highlighted the current lack of evidence for the additional benefit of GCS over and above the benefit of LMWH in surgical patients (8,9); further trials to address this matter have been called for (3).

If GCS were to offer a reduction in VTE risk over and above that afforded by LMWH, these benefits need to be weighed against a number of risks and disadvantages of GCS; these include (but are not limited to) discomfort, ischemia, rolling down and creating a constrictive band, blistering, cost, compliance issues, and the requirement for staff to assist patients in wearing. Indeed a large RCT in patients with stroke showed that routine care plus thigh-length GCS did not confer significantly more protection against VTE than routine care alone and was associated with significantly more harm (6). As a result, their use has already been limited in certain contexts. In addition to efficacy and risks, patients' experience may be impacted upon by the use of GCS. The annual cost of purchasing and applying GCS stockings to surgical inpatients assessed as being moderate or high risk for VTE in England is estimated at £63.1 million. This estimate does not include the further cost and time implications related to the identification and management of complications related to GCS. It is important that cost-effectiveness of this health technology is determined to ensure that NHS resources are correctly distributed. The results of this trial will support future guidance and policy in VTE prevention.

## 1.2 EVIDENCE EXPLAINING WHY THIS RESEARCH IS NEEDED NOW

Recent meta-analysis considering VTE rates in surgical patients receiving pharmaco-prophylaxis and GCS compared with pharmaco-prophylaxis alone (8), while containing a number of methodological shortcomings, concluded that evidence concerning "adding compression to anticoagulation reduces VTE risk is of low quality." To address some of the shortcomings, a systematic review has been undertaken aiming to summarise and assess the quality of existing evidence concerning the benefits of GCS in addition to prophylactic dose pharmaco-prophylaxis in inpatients across all surgical specialties, including orthopaedics (9). Inclusion criteria were: RCTs published within the last 10 years, surgical inpatients, a study arm examining prophylactic dose pharmacological thromboprophylaxis alone (including low molecular weight heparin, fondaparinux, or unfractionated heparin), a study arm examining prophylactic dose pharmacological thromboprophylaxis in conjunction with GCS, and outcome of VTE. A heterogeneity analysis was conducted concerning rates of VTE in the included study arms. 1025 articles were screened of which 27 RCTs were included (7,11-33). Six RCT study arms included patients with GCS in conjunction with prophylactic dose pharmacological thromboprophylaxis, whilst 22 RCT study arms included patients treated with prophylactic dose pharmacological thromboprophylaxis alone. Only one RCT had both its' study arms included in the systematic review. Total number of patients that received prophylactic pharmacological thromboprophylaxis alone was 12,481. Of these patients, 1,292 (10.4%) suffered VTE. The total number of patients that received GCS in

conjunction with prophylactic pharmacological thromboprophylaxis was 1,283. Of these patients, 75 had VTE (5.8%). Heterogeneity analysis demonstrated that the results of included study arms were significantly heterogeneous, precluding calculation of the usual meta-analytic summary estimates. The additional benefit of GCS to pharmacological thromboprophylaxis in surgical inpatients is not clear based on existing data. There is sufficient uncertainty to conduct a trial to examine whether GCS further reduces VTE incidence in surgical patients receiving prophylactic dose LMWH. Overall, systematic review and meta-analysis data have highlighted the current lack of evidence for the additional benefit of GCS over and above the benefit of LMWH in surgical patients (8,9); further trials to address this matter have been advised (3).

The VTE risks need to be balanced against the risks of preventative measures, both mechanical and pharmacological. Patient experience of stockings in the 'real world' is poor. In particular, the use of GCS is known to be associated with a number of undesired effects for the patient, including discomfort, ischemia, rolling down and creating a constrictive band, blistering. Previously, national stroke guidelines on VTE prevention extrapolated from small trials showing that GCS reduce the risk of DVT (6). The large randomised CLOTS 1 trial found no significant difference in symptomatic or asymptomatic femoro-popliteal DVT in individuals admitted to hospital with acute stroke (6). Importantly, CLOTS 1 also identified that skin breaks, ulcers, blisters, and skin necrosis were significantly more common in patients allocated to GCS than in those allocated to avoid their use (6). The widespread use of GCS has already been challenged and (3,4) limited in certain contexts, for example stroke patients. In view of the efficacy of GCS as an adjunct to LMWH in VTE prevention in surgical patients being poorly defined, GCS being responsible for complications and the enormous healthcare costs associated with their use, sufficient uncertainty is achieved to conduct a trial to examine whether GCS further reduces VTE incidence in surgical patients receiving prophylactic dose LMWH. There remains (despite guidelines) some variation in practice across the UK. We are aware of one centre, Salisbury District Hospital, which over the past three years has adopted a pharmacological prophylaxis policy (without GCS) that has been used for high risk surgical patients (n=249). In Salisbury, the incidence of hospital-acquired thrombosis is 1.3-2.9 per 1000 admissions, which is comparable to centres elsewhere in the UK (Kings College Hospital 3.83 per 1000 admissions) (34). As such, both patients and the health service stand to benefit from evidence to support the safe rationalisation of the use of GCS as a health technology. In this trial, all participants will receive effective thromboprophylaxis in the form of low dose (prophylactic rather than therapeutic) LMWH. This pharmacological strategy is used exclusively for groups where GCS are already contraindicated (for example peripheral arterial disease) or where evidence-based guidelines do not recommend their use (for example stroke patients (6)). A

number of major international guidelines currently recommend mechanical thromboprophylaxis as an alternative to pharmacological thromboprophylaxis for patients at moderate risk of VTE (35,36), stating that pharmacological thromboprophylaxis ‘may be combined with mechanical methods ... particularly in the presence of multiple risk factors’ (35). The Caprini scoring system, used in the United States, currently recommends that in higher risk group patients mechanical thromboprophylaxis is optional (37). At all times, the decision as to whether to randomise participants will be guided by the “uncertainty principle”, whereby the managing clinician should be substantially uncertain as to whether a patient will benefit from either the prescription or non-prescription of GCS.

### 1.3 RATIONALE FOR CURRENT TRIAL

The aim is to determine whether low dose low molecular weight heparin (LMWH) alone is non-inferior to a combination of graduated compression stockings (GCS) and low dose LMWH for the prevention of venous thromboembolism (VTE) adult elective surgical inpatients identified as being at moderate and high risk for VTE. The primary clinical objective is to compare the VTE rate in elective surgical inpatients receiving GCS and LMWH, compared with LMWH alone.

The primary health economic objective is to calculate the cost-effectiveness with regards the use of GCS in addition to prophylactic dose LMWH in elective surgical patients identified as being at moderate and high risk for VTE. Other objectives include:

- To determine the experience of surgical patients receiving LMWH and those receiving both GCS and LMWH.
- To profile the adverse effects of GCS and LMWH anticoagulation in this context.
- To support future guidance and policy in VTE prevention.

## 1. IMPACT

The impact of this trial will include:

- Determination whether, in moderate and high risk surgical inpatients, low dose LMWH alone is non-inferior to low dose LMWH in combination with GCS.

- Determination of the cost-effectiveness with regards the use of GCS in addition to prophylactic dose LMWH in moderate and high-risk surgical patients.
- Refining our understanding of the current VTE risk in moderate and high risk surgical patients in the era of modern preventative treatment.
- Profiling of the experience of surgical patients receiving LMWH and those receiving both GCS and LMWH.
- To profile the adverse effects of GCS and LMWH anticoagulation in this context.
- The opportunity to re-examine the VTE guidelines considering these findings. The Briefing Papers and other outputs directed at the NHS, professional bodies and professionals are expected to influence both future policy and practice. If GCS were found not to offer additional reductions in VTE risk in individuals given prophylactic dose LMWH, this would negate the need for GCS in this patient group, namely moderate and high risk surgical patients receiving LMWH. This would eliminate the side effects of this treatment in these patients and reduce the cost burden of GCS in surgical NHS patients; this has been estimated to be approximately £63.1 million per annum in England.

## 2. TRIAL OBJECTIVES

### 2.1 PRINCIPAL RESEARCH QUESTION

In surgical inpatients determined to be at moderate or high risk for VTE, is low dose LMWH alone non-inferior to low dose LMWH in combination with GCS?

The trial is a pragmatic, multicentre randomised clinical trial with adult surgical inpatients assessed by the ubiquitous Department of Health VTE assessment tool (38) as being at moderate or high risk randomised 1:1 to either:

- Current 'standard' combined low dose LMWH with GCS mechanical thromboprophylaxis, or
- Low dose LMWH pharmacoprophylaxis alone

### 3. TRIAL DESIGN

[figure not shown]
A multicentre, prospective, non-inferiority, group sequential randomised clinical trial to compare VTE outcomes in surgical inpatients assessed as being at moderate or high risk who are prescribed GCS in addition to low dose LMWH and those prescribed low dose LMWH alone.

Eligible and consenting moderate and high risk surgical patients will be computer randomised 1:1 to receive either prophylactic dose LMWH and GCS (or prophylactic dose LMWH alone (from point of admission. Each trial centre will be encouraged to use the LMWH+/-GCS regimen that has been adopted and established locally. Either below-knee or above-knee compression stockings may be used; and the inclusion of obese patients or those undergoing bariatric surgery will be allowed. We recommend that LMWH be given at 1800hrs daily, including the evening before surgery (if admitted the night before surgery) except those undergoing regional anaesthesia. Post-operatively, LMWH, and GCS when randomised, should be continued until discharge as this is less subjective than until 'ambulant'.

[figure not shown]
#### 3.1 HEALTH TECHNOLOGIES BEING ASSESSED

Graduated elastic compression stockings (GCS) for thromboprophylaxis in elective surgical patients receiving prophylactic dose LMWH. These GCS are standard, widely available, and the optimal gradient of pressure has previously been shown to be 18mmHg at the ankle, 14mmHg at the calf, and 10mmHg at the knee (39). This technology is not subject to rapid change.

The trial was originally scheduled to take 36 months

In April 2018 the HTA approved a 12 month time only extension (at no additional cost) to enable sites to recruit to target.

## 3.2 TRIAL OUTCOME MEASURES

### 3.2.1 Primary Endpoint

VTE within 90 days { duplex ultrasound-proven new lower-limb DVT up to 90 days post-surgery (symptomatic or asymptomatic) + symptomatic PE (imaging confirmed) up to 90 days post-surgery} The 90 day endpoint is in line with the NHS Standard Contract for Acute Services which specifies that root cause analysis should be performed for all cases of hospital-associated VTE – defined as cases arising within 90 days of a hospital stay (40).

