### 3.2.3 Measurement of outcomes

### 3.2.3.1 Primary outcome measure

Telephone, online or face-to-face (according to participant preference) at one week post-surgery or at discharge, and at 90 days. Proceeding to imaging at these points if there is clinical suspicion of a DVT or PE. Routine bilateral full lower limb duplex ultrasonography at between 14 days and 21 days post-operatively to capture peak VTE incidence (41,42). We expect to capture >95% of VTE since the average time-point for DVT is 7 days and PE is 21 days, with vast majority events being DVT. However, data from duplex scans outside this window will be collected and subsequently analysed.

The range of dates is to prevent restricting scanning to a single date. Routinely scanning participants only once reduces cost, and limits the time and inconvenience to the enrolled trial subjects (ethical consideration, improve recruitment and reducing dropouts and loss to follow-up). No pre-operative duplex for these same reasons and also because asymptomatic pre-operative DVTs should be accounted for by equal distribution in the two trial arms by the randomisation process. If participants are inpatients at the time of their routine bilateral full lower limb duplex ultrasonography at between 14 days and 21 days postoperatively, or if any inpatient duplex imaging is prompted by clinical suspicion, GCS will be removed prior to imaging to ensure optimum blinding of those undertaking the imaging (6). If clinical VTE is confirmed on investigation at any point within 90 days, this will be recorded. The 90 day endpoint is in line with the NHS Standard Contract for Acute Services which specifies that root cause analysis should be performed for all cases of hospital-associated VTE – defined as cases arising within 90 days of a hospital stay (40).

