### 3.2.3.2 Secondary outcome measures

Generic quality of life will be assessed at baseline, upon discharge and at follow-up (both 14-21 days and 90 days) using the EQ-5D. EQ-5D is widely used and well validated, and is currently employed as part of the routine collection of Patient Reported Outcome Measures (PROMs) for the NHS in England (43).

Compliance with stockings will be addressed; participants will be issued with a VTE diary where they can document their GCS use, as well as any adverse outcomes related to GCS or LMWH use.

Compliance with LMWH will be assessed by review of the participant's medication chart by the local research nurse or study coordinator.

Mortality will be recorded however, it is anticipated that this will be very low.

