All randomised participants will undergo a routine bilateral full lower limb duplex ultrasonography between 14 and 21 days post operatively to identify VTE. An anonymised copy of the duplex will be collected and forwarded to the Study Coordinating Centre, Imperial College London. We expect to capture >95% of VTE since the average time-point for DVT is seven days and PE is 21 days, with vast majority events being DVT. The range of dates is to prevent restricting scanning to a single date. EuroQuol 5D (EQ5D) generic quality of life assessment will also be administered at this visit.

## 6.4 FOLLOW-UP VISIT 3

Participants will be seen in person or contacted by telephone or online (according to participant preference) at 90 days post surgery.

Recorded assessments will include:

- Any diagnosis of VTE (Anonymised copies of any duplexes will be forwarded to the Study Coordinating Centre, Imperial College London)

- Any symptoms or signs of VTE (if there is clinical suspicion identified by the research nurse which has not been identified by the clinical team, the research nurse will inform the clinical team who will proceed to imaging if appropriate).
- EuroQuol 5D (EQ5D) generic quality of life assessment
- Review of participant VTE diary (completed until 90 days)
- Collection of Adverse or Serious Adverse Events

If clinical VTE confirmed on investigation at any point within 90 days, this will be recorded

- Symptomatic DVT
- Asymptomatic DVT identified by duplex
- Imaging-confirmed symptomatic PE

Any participant with asymptomatic (or symptomatic) DVTs identified by duplex ultrasound will proceed to being treated as per local guidelines for the management of DVT.

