## **6.6 DEFINITION OF END OF PARTICIPANTS PARTICIPATION**

The end of the participants participation is defined as 90 days from the date of the index elective operation.

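### A PE proven only at post-mortem cannot enter the primary endpoint, and the protocol does not settle whether day 90 limits the onset or the confirmation of VTE

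*Protocol*

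**What the plan says.** The primary endpoint, in the trial summary and in section 3.2.1, has two components. One is new lower-limb DVT proven by duplex, with or without symptoms. The other is "symptomatic PE (imaging confirmed) up to 90 days post-surgery". Section 6.4 lists what is recorded: symptomatic DVT, asymptomatic DVT found by duplex, and symptomatic PE confirmed by imaging. Neither post-mortem confirmation nor review of cause of death is mentioned anywhere.

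Deaths enter as overall mortality, a secondary outcome in the trial summary that is missing from the list in section 3.2.2. Section 3.2.3.2 says: "Mortality will be recorded however, it is anticipated that this will be very low". Deaths are also reportable as serious adverse events (sections 5.1 and 5.3.2).

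On timing, section 3.2.3.1 plans contacts at one week or discharge and at 90 days, and adds: "Proceeding to imaging at these points if there is clinical suspicion of a DVT or PE". The same section says: "If clinical VTE is confirmed on investigation at any point within 90 days, this will be recorded". Section 6.4 repeats this: "If clinical VTE confirmed on investigation at any point within 90 days, this will be recorded". Section 6.6 then states: "The end of the participants participation is defined as 90 days from the date of the index elective operation".

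**The concern.** Section 1.1 gives the reason for preventing VTE: "VTE encompasses a range of clinical presentations, including pulmonary embolism, and is an important preventable cause of death in hospitalized patients". Yet a PE that kills before any imaging, and is then proven at post-mortem, does not meet the endpoint as worded. If that death comes before the day 14 to 21 scan, there is no screening duplex either. The missed event would be a failure of prophylaxis of the most serious kind.

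The last contact is a planned trigger for imaging. If day 90 limits confirmation, much of what that contact prompts could not count; if it limits onset, it could. Sites and analysts could apply either rule.

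The direction matters because this is a non-inferiority comparison on an absolute margin. Uncounted events shrink the observed difference while the margin stays fixed. Recruitment is now confined to high-risk patients aged 65 or over, and section 7.1.2 implies only about 33 events there.

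**Working it through.** **1. Routes into the endpoint for a participant who dies of PE**

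| Situation | Result under sections 3.2.1 and 6.4 |
|---|---|
| PE imaged before death | Counts |
| Duplex-proven DVT before death | Counts |
| No imaging, PE proven at post-mortem | No route; no event or missing |

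The protocol does not say which of the last two applies. Scored as no event, the PE is lost outright. If it is treated as missing, the only method the protocol names is multiple imputation under missing at random (section 7.2.1, original analysis). That would give the participant roughly the risk of similar participants, about 0.036 of an event in subpopulation 4, where the truth is 1.

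**2. The two clocks**

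- Onset: section 3.2.1 attaches the 90 days to the DVT or PE itself. Sections 3.2.1 and 3.2.3.1 justify the window by an NHS definition based on when cases arise.
- Confirmation: sections 3.2.3.1 and 6.4 record VTE that has been confirmed by investigation within 90 days.
- Contact: it takes place at 90 days, possibly by telephone or online, with no visit window (section 6.4). Imaging on suspicion follows (section 3.2.3.1, section 6.4, Appendix 1).
- End of participation: day 90 (section 6.6).

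The sentence in section 3.2.3.1 on duplex scans taken outside the window follows the description of the routine day 14 to 21 scan. It concerns duplex only and does not settle the point.

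**3. Size**

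Inputs from section 7.1.2: 912 participants, event rate 3.6%, margin 4.0 points, one-sided 2.5%, power 90%. Allocation is 1:1.

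The plan's figure reproduces:

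n per arm = (1.960 + 1.282)² × 2 × 0.036 × 0.964 / 0.04² = 455.8, so 456 per arm and 912 in total.

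Expected events: 912 × 0.036 = 32.8.

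Loss from one arm only:
- one event: 1/456 = 0.22 points, which is 0.22/4.0 = 5.5% of the margin
- two events: 2/456 = 0.44 points, or 11% of the margin.

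Equal proportional loss, with true rates at the margin (3.6% and 7.6%) and a share f of events uncounted in both arms:
- observed difference = 0.04 × (1 − f)
- type I error = Φ[(0.04 − 0.04(1 − f))/SE − 1.96], where SE uses the reduced rates with 456 per arm.

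For f = 3% the rates are 3.492% and 7.372%. SE = √[(0.03492 × 0.96508 + 0.07372 × 0.92628)/456] = 0.01496. Then 0.0012/0.01496 = 0.080, and Φ(−1.88) = 3.0%.

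True events at the margin number 456 × (0.036 + 0.076) = 51.1, which gives the middle column.

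| Share lost (assumed) | Events lost, of 51.1 | One-sided type I error |
|---|---|---|
| 0% | 0 | 2.5% |
| 1% | 0.5 | 2.7% |
| 3% | 1.5 | 3.0% |
| 5% | 2.6 | 3.4% |
| 10% | 5.1 | 4.6% |

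**The case against.** An objective, imaging-based endpoint is a sound choice in an open trial that relies on blinded imaging staff (section 6.5). Attributing deaths to PE by judgement would bring back the subjectivity the design avoids. That stands, and it is why the remedy should stop at post-mortem proof.

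It can also be said that the classification of deaths belongs in the SAP, which is not available here. That answers how missing outcomes are handled. It does not answer the definition: the protocol itself fixes what counts as a PE, and the wording leaves out post-mortem proof.

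The protocol expects very low mortality, expects nearly all events to be DVT, and expects to capture more than 95% of VTE (section 3.2.3.1). So few participants are likely to be affected. That stands too.

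Three stronger readings are tempting, and the documents do not support them.
- A reader might infer that VTE suspected at day 90 and imaged later is excluded. No section says so. Section 3.2.1 points towards onset, and planning imaging at that contact suggests it was meant to count. This is a conflict, not a stated exclusion.
- A reader might infer that fatal PE as such is dropped. Only fatal PE without imaging, in a participant without duplex-proven DVT, is affected.
- A reader might take two lost events as a serious threat. At 3.6% in both arms the 95% half-width is 1.96 × √(2 × 0.036 × 0.964/456) = 2.42 points. That leaves 4.0 − 2.42 = 1.58 points, or about 7.2 events, and 2/7.2 = 28%. The arithmetic is right, but it puts both losses in the LMWH-alone arm, although the rule applies to both arms and no document supplies the count.

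**Conclusion.** The post-mortem gap holds on the protocol's wording: followed as written, a PE proven only at post-mortem is scored as no event or as missing. The day-90 issue holds as an unresolved inconsistency between onset and confirmation.

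The effect is probably small and its frequency cannot be derived from the protocol. The 0.22 points per event assumes 456 analysed per arm and loss from one arm only. The type I error of about 3.0% assumes that 3% of events are lost equally and that the true difference sits at the margin. Either way the tilt is towards non-inferiority, modestly. The sample size of 912 is unaffected. The wording should be corrected; the trial's conclusions are not shown to be at risk.

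**What to change.** 1. In section 3.2.1 and the trial summary, define the PE component as symptomatic PE confirmed by imaging or at post-mortem. Add the matching category in section 6.4. Do not add deaths attributed to PE by judgement to the primary endpoint.
2. State that the 90-day limit applies to onset, so that VTE suspected at or before the day-90 contact and confirmed by the imaging it prompts is counted. Reconcile sections 3.2.3.1, 6.4 and 6.6 with this, so that the imaging result can still be collected. The documents supply no basis for a particular grace period.
3. Add a sensitivity analysis of VTE or death from any cause by day 90, using mortality already recorded.

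The cost is modest but real. Section 10 requires Sponsor, REC and R&D approval for an amendment, and Appendix 3 has recruitment and follow-up running only to April 2019. The protocol does not say that post-mortem reports are collected, so they would have to be sought for the deaths. For participants already past day 90, late imaging can be counted only where the result can still be obtained. The sensitivity analysis will be diluted by deaths unrelated to VTE and should be read as support for the primary result. The change should be made before outcomes by arm are seen outside the iDMC.
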